| 11 | 🗌 Right Side | 🗌 Left Side | | Πu | Inknow | /n | | |] N// | A | |
| 12 | 🗌 Right Side | 🗌 Left Side | | Πu | Inknow | /n | | C | N// | A | |
| Previous Neu | IROVASCULAR P RO | CEDURES | | | | | | | | | |
| 34. Carotid ste | nt placement | | 🗌 Yes | | | 0 | | | Unk | nown | |
| 35. Carotid end | larterectomy | | 🗌 Yes | | | 0 | | | Unk | nown | |
| 36. Prior treatr target | nent of aneurysm o | other than | 🗌 Yes | | □ N | 0 | | | Unk | nown | |
| 36.1 Spec | ify Treatment(s) | | 🗌 Intra | crani | al coils | | | | | | |
| | | | 🗌 Othe | er dev | /ice, sp | ecify | : | | | | |
| | | | | er trea | atment | :, spe | city: |   | | | |
| 36.2 Date | of most recent pro | ocedure | | / | | | | / | | | |
| 37. Other neur | ovascular procedui | re(s) | 🗌 Yes | | | 0 | | | Unk | nown | |
| 37.1 Spec | ify type of procedu | ıre(s) | 1) | | | | | | | | |
| | | | 2) | | | | | | | | |
| | | | 3) | | | | | | | | |
| | | | 4) 5) | | | | | | | | |
| 37.2 Date | of most recent pro | ocedure | | / | | | |]/[| | | |
| 38. Date target | lesion discovered | CERUS CO | | | | | |]/[| | Pa | ge of |

| Cerus Endovascular | Document Number DNX099-01 | Rev F | Page 100 of 106 |
|----------------------------|---|---------------|-----------------|
| Investigational Protocol | Title | | |
| Confidential & Proprietary | Contour Neurovascular System [™] European Pre-M Study (CERUS) | 1arket Unrupt | ured Aneurysm |

Page of 42

| Cerus Endovascular | Document Number DNX099-01 | Rev F | Page 101 of 106 |
|----------------------------|--|---------------|-----------------|
| Investigational Protocol | Title | | |
| Confidential & Proprietary | Contour Neurovascular System TM European Pre-M Study (CERUS) | 1arket Unrupt | ured Aneurysm |

| GLASCOW COMA SCALE (GCS) | |
|--|------------|
| | Not done |
| | |
| Exam Date | |
| Performed by | |
| GCS Total Score | 3 - 15 |
| Modified Rankin Scale (MRS) | □ Not done |
| Exam Date | |
| Performed by | |
| mRS Grade | 0 - 6 |
| NIH STROKE SCALE (NIHSS) | □ Not done |
| Exam Date | |
| Performed by | |
| NIHSS Total Score | 0 - 42 |
| Subject sedated for exam | □Yes □No |
| Subject intubated and paralyzed for exam | Yes No |

| Cerus Endovascular | Document Number DNX099-01 | Rev F | Page 102 of 106 |
|----------------------------|---|---------------|--------------------|
| Investigational Protocol | Title | | |
| Confidential & Proprietary | Contour Neurovascular System [™] European Pre-M Study (CERUS) | larket Unrupt | ured Aneurysm |

| | | 6 |
|-------------|--------------------|-------------|
| | | |
| | | |
| | | |
| | | |
| | | |
| | | |
| | | |
| | | |
| | | |
| | | |
| | | |
| | | |
| | | |
| | | |
| | | |
| | | |
| | | |
| | | |
| | | |
| | | |
| | | |
| | | |
| | | |
| | | |
| | | |
| | | |
| | | |
| | | |
| | | |
| | | |
| | | |
| | | |
| | | |
| | | |
| | | |
| | | |
| | | |
| | | |
| | | |
| | | |
| | | |
| | | |
| | | |
| | | |
| | | |
| | | |
| | | |
| | | |
| | | |
| | | |
| | | |
| | CERUS CONFIDENTIAL | |
| DNX099-F1 B | 04 May 2018 | Page of 42 |
| 510,00011.5 | 04 may 2010 | 1 490 01 12 |
| | | |

| Cerus Endovascular | Document Number DNX099-01 | Rev F | Page 103 of 106 |
|----------------------------|---|---------------|-----------------|
| Investigational Protocol | Title | | |
| Confidential & Proprietary | Contour Neurovascular System [™] European Pre-M Study (CERUS) | 1arket Unrupt | ured Aneurysm |

Page of 42

| Cerus Endovascular | Document Number DNX099-01 | Rev F | Page 104 of 106 |
|----------------------------|--|---------------|--------------------|
| Investigational Protocol | Title | | |
| Confidential & Proprietary | Contour Neurovascular System TM European Pre-M Study (CERUS) | 1arket Unrupt | ured Aneurysm |

| Cerus Endovascular | Clinical Study of the | Site Numb∍r |
|---|--|-------------------------------|
| | BASELINE ANGIOGRAM | |
| | | |
| | | |
| | | |
| | | |
| BASELINE ANGIOGRAM | Not Done | |
| | | |
| An angiogram of the target aneurysm and | l parent vessel must be performed within 3 mon | ths of Enrollment |
| 1. Date of Angiogram | | |
| 2. Angiogram performed by | | |
| 3. Target IA Type Sidewall | Bifurcatio | n or Terminal Other, speci |
| 4. Target IA Width mm | | |
| 5. Target IA Neck mm | | |
| 6. Target IA Height mm | | |
| 7. Evidence of ruptured IA | Yes No | |
| | | |
| | | |

| Cerus Endovascular | Document Number DNX099-01 | Rev F | Page 105 of 106 |
|----------------------------|---|---------------|-----------------|
| Investigational Protocol | Title | | |
| Confidential & Proprietary | Contour Neurovascular System [™] European Pre-M Study (CERUS) | 1arket Unrupt | ured Aneurysm |

| Cerus Endovascular | Document Number DNX099-01 | Rev F | Page 106 of 106 |
|----------------------------|---|----------|--------------------|
| Investigational Protocol | Title | | |
| Confidential & Proprietary | Contour Neurovascular System TM European Pre-Market Unruptured Aneurysm Study (CERUS) | | |

Page of 42

Study Purpose:	Cerus Endovascular is sponsoring a prospective, multi-center trial to document the safety and performance of the Contour Neurovascular System [™] ("Contour"). The purpose of the study is to document safety and performance of the Contour in treatment for patients with intracranial aneurysms (IA). The data from the study will be reported as a Pre-Market study to the Notified Body to support CE Mark approval.
Study Design:	The study is a prospective, single arm, multi-center study.
Objective and Endpoints:	The primary objective of this study is to document the safety and performance of the Contour Neurovascular System. The data from the study will be reported as a Pre-Market study to the Notified Body to support CE Mark approval. In addition, the data may be used to support US approval by the Food and Drug Administration (FDA) to market the Contour device in the United States. 1. Primary Safety Endpoint: The proportion of subjects with death of any non-accidental cause or any major disabling stroke within the first 30 days after treatment or major disabling stroke or death due to neurological cause from day 31 to 6 months after treatment. Note: Major Disabling Stroke is defined as an episode of neurological signs or symptoms that persist beyond 24 hours accompanied with evidence of ischemia/infarction on imaging that results in an increase of NIHSS from baseline by ³ 4 points and/or an increase from mRS baseline by >2. 2. Primary Performance Endpoint: To demonstrate the occlusion rate on the 6 month angiogram as adjudicated by a core laboratory. Success will be defined as complete occlusion demonstrated by a

Cerus Endovascular	Document Number DNX099-13	Rev A	Page 5 of 9
Statistical Analysis Plan	Title Statistical Analysis Plan for: Contour Neurovascu	lar System TM	European
Confidential & Proprietary	PreMarket Unruptured Aneurysm Study (CERUS))	Duropeun

Secondary Measures	Additional measures will be summarized:	
	 Secondary Safety: Serious Adverse Events (SAE) associated with the procedure or device All serious neurological adverse events 	
	 Secondary Performance: Detailed assessment of aneurysm occlusion from post procedure to 6months provided by the core lab review of the angiogram (DSA) including the following: Raymond Roy scale Modified Web Occlusion Scale Percent Occlusion Device Stability Rate of retreatment Summary of device performance including the following: Time required for implantation of the Contour Device sizes used Number of attempts to deploy the device Number of failed implant attempts Any reports of device deficiencies 	
Number of Sites:	A maximum of 10 European investigational sites will participate.	
Sample Size:	A maximum of 35 subjects will be enrolled to obtain follow-up data for the primary analysis for 30 subjects while allowing for attrition to be submitted for CE Mark application.	
Patient Population:	The patient is enrolled at the time of consent and is considered a study subject in the reporting analysis group only when the patient is fully qualified and at least one Contour device has been placed into the patient's body.	
Study Visits:	Baseline, procedure, discharge, 1 month, 6 months and 12 months.	

Cerus Endovascular	Document Number DNX099-13	Rev A	Page 6 of 9
Statistical Analysis Plan	Title Statistical Analysis Plan for: Contour Neurovascular System TM European		
Confidential & Proprietary	PreMarket Unruptured Aneurysm Study (CERUS))	Duropour

Study Oversight:	Both a CEC and DSMB will be employed for study oversight and will meet as a combined committee. The CEC will review and classify all neurologic, devicerelated and procedure-related SAEs to ensure they are reported accurately. The DSMB will review the study data after enrollment of the first five patients. Enrollment of further patients will occur as the DSMB reviews the data. The DSMB will provide a report following the review and advise Cerus Endovascular for any modifications or concerns that may be necessary. The DSMB will provide further evaluation at least twice per year and after the first 5 patients are enrolled.
	If slow enrollment occurs, the DSMB may meet less frequently.

5 Analysis Population

Two patient populations will be considered in the analyses, an Intent-to-Treat (ITT) population and a Per Protocol population (PP). The ITT population includes all patients. The PP population will include subjects who complete 6 months of follow-up, die prior to their 6-month clinic visit, or are study failure (withdrawal from study to obtain alternate treatment). The PP will exclude patients with any major protocol violation that affects proper study inclusion or significant outcomes. Endpoints will be evaluated in the PP and ITT populations.

Any patient for whom a failed implant attempt is performed will be followed for 1 month, or until resolution of any potential device or implanted related adverse events, whichever occurs last.

Any patient who is consented but has no implant attempt will be study exited.

6 General Statistical Principles

The analysis for all primary and secondary study endpoints and baseline, procedural and follow-up characteristics will be performed on an intent-to-treat analysis population which will include all available data for all enrolled subjects. Standard summary statistics will be calculated for all study variables. For continuous variables, statistics will include means, standard deviations, medians and ranges. Categorical variables will be summarized in frequency distributions. Missing data will not be imputed. The number of data values available for each analysis will be reported so that the impact of missing data can be seen.

Statistical analyses will be conducted in SAS version 9.4 or above (SAS Institute, Cary, N.C.).

Cerus Endovascular	Document Number DNX099-13	Rev A	Page 7 of 9	
Statistical Analysis Plan	Title Statistical Analysis Plan for: Contour Neurovascular System [™] European PreMarket Unruptured Aneurysm Study (CERUS)			
Confidential & Proprietary				

7 Analysis of Study Endpoints

Primary Safety Endpoint

The primary safety endpoint will be calculated as the proportion of subjects with death of any nonaccidental cause or any major disabling stroke within the first 30 days after treatment or major disabling stroke or death due to neurological cause from day 31 to 6 months after treatment.

Where "Major Disabling Stroke" is defined as an episode of neurological signs or symptoms that persist beyond 24 hours accompanied with evidence of ischemia/infarction on imaging that results in an increase of NIHSS from baseline by ³ 4 points and/or an increase from mRS baseline by >2.

Primary Performance Endpoint

The primary performance endpoint will be calculated as the proportion of subjects with complete occlusion demonstrated with a Grade 1 on the Raymond Roy Scale at 6 months. The data will be as reported as analyzed by the core laboratory.

Secondary Safety Endpoints

- Serious Adverse Events (SAE) associated with the procedure or device will be calculated as the proportion of subjects with at least one SAE and each individually reported SAE. Event counts will also be reported.
- Serious neurological adverse events will be calculated as the proportion of subjects with at least one serious neurological AE and each individually reported neurological AE. Event counts will also be reported.

Secondary Performance Endpoints

The secondary performance endpoints will be reported as analyzed by the core laboratory. The endpoints will be analyzed at the the 6-month post implant timepoint unless procedure-related.

- Raymond Roy scale: the endpoint will be calculated as the proportion of subjects with each category
- Modified Web occlusion scale: the endpoint will be calculated as the proportion of subjects with each category

Cerus Endovascular	Document Number DNX099-13	Rev A	Page 8 of 9	
Statistical Analysis Plan	Title Statistical Analysis Plan for: Contour Neurovacular System TM European			
Confidential & Proprietary	PreMarket Unruptured Aneurysm Study (CERUS)			

- Percent occlusion: the endpoint will be calculated as the mean and standard deviation or median and range depending on the normality of the data of the measured occlusion
- Device stability: the endpoint will be calculated as the proportion of subjects with stable device placement
- Retreatment: the endpoint will be calculated as the proportion of subjects with retreatment of the target aneurysm between the implant procedure and 6 month post implant timepoint
- Time required for implantation of the Contour: the endpoint will be calculated as the mean and standard deviation or median and range depending on the normality of the data
- Device size: the endpoint will be calculated as the proportion of subjects with each size of implanted Contour device
- Number of attempts to deploy the device: the endpoint will be calculated as the proportion of subjects with each number of implant attempts (e.g. 1, 2, 3)
- Number of failed attempts to deploy the device: the endpoint will be calculated as the proportion of subjects with each number of failed attempts (e.g. 1, 2, 3)
- Device deficiencies: the endpoint will be calculated as the proportion of subjects experiencing a device deficiency. Individual deficiency category counts will also be reported.

8 Additional Analyses

Subject accountability and discontinuation will be summarized for all subjects who are enrolled in the study.

A summary of subjects with protocol deviations will be reported but those subjects will be included in all analyses although endpoints may be summarized without the subjects (per-protocol analysis group) to provide additional information but not for the primary analysis.

Applicable summary tables of baseline and follow-up data points not included in the endpoint analyses as well as subject listings will be provided in summary reports.

No interim analyses are planned. Summary reports will be created to comply with regulatory requirements.

Cerus Endovascular	Document Number DNX099-13	Rev A	Page 9 of 9	
Statistical Analysis Plan	Title Statistical Analysis Plan for: Contour Neurovascular System [™] European PreMarket Unruptured Aneurysm Study (CERUS)			
Confidential & Proprietary				

9 Data Acquisition

Details for the data acquisition via an electronic database (EDC) are contained in the study-specific Data Management Plan.

10 Revision History

Rev	DCO	Change Description	Release Date
А	0458	Initial Release	01 Feb 2019

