7.10 Early Withdrawal

Reasons for subject withdrawal prior to study completion shall be documented. Valid reasons for early study withdrawal include:

- Death
- AE or other medical condition that prevents study participation
- Withdrawal of voluntary consent
- Lost to follow-up (LTF)
- Termination of Study

At least three documented attempts shall be made to contact any subject who is LTF.

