10.2 Patient Population

Two patient populations will be considered in the analyses, an Intent-to-Treat (ITT) population and a Per Protocol population (PP). The ITT population includes all patients. The PP population will include subjects who complete 6 months of follow-up, die prior to their 6-month clinic visit, or are study failure (withdrawal from study to obtain alternate treatment). The PP will exclude patients with any major protocol violation that affects proper study inclusion or significant outcomes. Endpoints will be evaluated in the PP and ITT populations.

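### The per-protocol set has no place for a stroke survivor who leaves early, so the supplementary per-protocol safety rate can lose an observed primary safety event

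*SAP*

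**What the plan says.** SAP 5 and Protocol 10.2 use the same definition. It opens: "The PP population will include subjects who complete 6 months of follow-up, die prior to their 6-month clinic visit, or are study failure". The parenthesis that follows limits study failure to "withdrawal from study to obtain alternate treatment". Subjects with a major protocol violation affecting inclusion or significant outcomes are then removed. SAP 5 adds "Endpoints will be evaluated in the PP and ITT populations" and exempts no endpoint.

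Protocol 7.10 lists the valid reasons for leaving early. Besides death and study termination they are "AE or other medical condition that prevents study participation", withdrawal of consent, and loss to follow-up. These last three are not routes into PP.

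The primary safety endpoint (SAP 7, Protocol 10.5.1) has a non-fatal component throughout. Up to day 30 it counts any major disabling stroke or non-accidental death. After that it counts "major disabling stroke or death due to neurological cause from day 31 to 6 months after treatment".

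On the role of the two sets, SAP 6 places all primary and secondary endpoints on an "intent-to-treat analysis population which will include all available data for all enrolled subjects". SAP 8 describes the other summary as "per-protocol analysis group) to provide additional information but not for the primary analysis"; Protocol 10.3 says the same.

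**The concern.** A rule based on completing follow-up suits the 6-month angiogram, because without the image there is no result. It suits the safety endpoint less well. A subject with a major disabling stroke on day 10 has already reached that endpoint, and nothing about the outcome is missing. If the deficit then leads to withdrawal, the PP rule removes the subject and the recorded event together. A fatal stroke on the same day would stay in. The rule therefore protects the fatal part of the composite but not the non-fatal part.

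The study tests no hypothesis (Protocol 10.7), and safety is left to clinical judgement of the collected data (Protocol 10). With about 30 subjects and few expected events, a reader will notice whether a table shows zero events or one. A PP rate of 0% beside a non-zero ITT rate could be taken as reassurance when the set definition alone produced it.

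**Working it through.** The plan states no safety rate, power or formal sample size, so there is no figure of its own to reproduce. The one related input is enrolment: up to 35 subjects to obtain 30 with follow-up (Protocol synopsis, SAP synopsis), which allows a loss of up to 5/35 = 14.3%. Event and withdrawal rates below are assumptions.

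**1. Apply the rule to three records.**

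| Record | Route into PP | Event counted in PP |
|---|---|---|
| A: fatal stroke, day 10 | Death before the 6-month visit | Yes |
| B: non-fatal major disabling stroke, day 10; completes 6 months | Completion | Yes |
| C: same stroke, day 10; leaves at month 2 because of the deficit | None | No |

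**2. Effect of one record C.** For any e < n, e/n < (e+1)/(n+1), so dropping a subject with an event lowers the rate relative to keeping that subject. With 30 subjects and one event, 1/30 = 3.3% (exact 95% CI 0.1 to 17.2%) becomes 0/29 = 0% (0 to 11.9%).

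**3. PP against ITT.** Assume 35 enrolled, 5 early leavers, one of whom had a stroke, and e events among the 30 retained.

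| e | PP as written | PP with the event subject kept | ITT |
|---|---|---|---|
| 0 | 0/30 = 0.0% | 1/31 = 3.2% | 1/35 = 2.9% |
| 1 | 1/30 = 3.3% | 2/31 = 6.5% | 2/35 = 5.7% |
| 2 | 2/30 = 6.7% | 3/31 = 9.7% | 3/35 = 8.6% |

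PP stays below ITT up to e = 5; the two meet at e = 6 (6/30 = 7/35 = 20%). If no leaver had an event, the order reverses: with e = 1, PP is 1/30 = 3.3% and ITT is 1/35 = 2.9%.

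**4. Chance of losing at least one event.** Let p be the rate of non-fatal primary safety events and q the share of those subjects who leave for a reason other than alternate treatment. Among 30 subjects the chance is 1 − (1 − pq)^30.

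| p | q = 20% | q = 50% |
|---|---|---|
| 5% | 1 − 0.990^30 = 26% | 1 − 0.975^30 = 53% |
| 2% | 1 − 0.996^30 = 11% | 1 − 0.990^30 = 26% |
| 1% | 1 − 0.998^30 = 6% | 1 − 0.995^30 = 14% |

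Protocol 6.1 puts ischemic CVA of any severity below 5%. Major disabling stroke also needs an NIHSS or mRS change, so 5% is at the upper end.

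**5. Expected PP rate.** Let d be the share of event-free subjects who leave. The expected rate is approximately p(1−q) / [p(1−q) + (1−p)(1−d)]. At p = 5%:

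- d = 0: 0.040/(0.040 + 0.950) = 4.0% for q = 20%; 0.025/(0.025 + 0.950) = 2.6% for q = 50%.
- d = 14.3%, so (1−p)(1−d) = 0.950 × 30/35 = 0.814: 0.040/0.854 = 4.7% for q = 20%; 0.025/0.839 = 3.0% for q = 50%.

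When q equals d, the expression returns p and there is no bias.

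**The case against.** The strongest reply is that no primary result depends on this. ITT uses all available data, so record C's stroke stays in the primary safety rate, and both documents call the PP summary additional information. The event also remains visible elsewhere. The clinical events committee adjudicates neurologic SAEs (Protocol 9.1), serious neurological events are reported by subject and by event count (SAP 7), and discontinuations are summarised and subject listings provided (SAP 8). All of this stands, and it keeps the severity low. It does not correct the PP rate itself.

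A second reply is that SAP 8 and Protocol 10.3 describe the PP group differently, as the subjects left after removing those with protocol deviations. On that description a stroke subject who withdraws without a deviation would stay in. This is a fair point, but SAP 5 and Protocol 10.2 are the sections that define the set, and nothing says that the looser description overrides them. Record C is therefore not clearly restored.

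A third reply concerns direction. A reader might infer that the PP safety rate is always too low. The documents do not support that: the same rule drops event-free leavers, which pushes the rate up, as step 3 shows. The expected rate falls only if stroke subjects leave more often than others. That is plausible for a disabling event, but it is not established. Allowing for loss among event-free subjects also cuts the expected shortfall at p = 5% and q = 20% from 1.0 to about 0.3 points.

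**Conclusion.** The gap in the definition is real. A subject with an observed non-fatal major disabling stroke who leaves before 6 months, other than for alternate treatment, drops out of the PP safety rate together with the event. At this sample size one such record is worth about 3 percentage points and can turn one event into none.

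The consequence is conditional and confined to a supplementary summary. It needs a stroke followed by early departure, and the chances in step 4 rest on assumed event and withdrawal rates that the documents do not supply. A reader might infer that the trial's safety result is understated; it is not, because the ITT analysis retains the event. Low severity, but worth correcting before the PP table is produced.

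**What to change.** Amend SAP 5 and Protocol 10.2 in one of two ways.

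- **Option 1.** Report the primary safety endpoint only on the ITT/treated set, and keep PP for the angiographic endpoint. This removes the problem.
- **Option 2.** Add a further route into PP for the safety endpoint: *or have a primary safety endpoint event as defined in SAP 7, whatever the later follow-up status*. The reference to SAP 7 matters because after day 30 only neurological deaths count, so a phrase covering all non-accidental deaths up to 6 months would misstate the endpoint. Show this rate beside the ITT rate, with the number of event-free early leavers.

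The cost is one sentence in each document and no new data. Under option 2 the PP safety rate becomes slightly less favourable. It may also lie slightly above ITT, because event-free leavers stay excluded: 2/31 = 6.5% against 2/35 = 5.7% in the step 3 example with e = 1. In expectation, at p = 5% and d = 14.3%, it is 0.050/(0.050 + 0.814) = 5.8% against 5%. This is why the ITT rate and the count of event-free leavers should appear alongside it.

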- The patient is not considered enrolled but not included in the primary analysis group in the study: if at the onset of the procedure in the initial DSA, the investigator determined the patient's IA was not suitable for treatment with the device, thus, no attempt was made by the investigator to place the device. The patient will be treated outside of the study per the investigator's usual practices. The reason for not treating the patient must be documented on a study exit form. The patient is not included in the primary analysis group because the Contour was never opened or deployed inside the patient. All patients will be listed in the final report. The patient is considered enrolled but not included in the primary analysis group in the study: at the onset of the procedure, the investigator attempted but was unable to place the device within the IA and the subject required alternative treatment. The subject is considered enrolled for the purposes of the study but will only be followed through the 1-month visit. All failed implant attempts will be reported in the final report.
- The patient is considered enrolled and included in the primary analysis group in the study: if at the onset of the procedure, the investigator determined the subject's IA was suitable for treatment with the device. The investigator successfully placed the device within the IA. The subject is considered enrolled for the purposes of the study and will be followed for the duration of the study.
- The patient is considered enrolled and included in the primary analysis group in the study: if at the onset of the procedure, the investigator determined the subject's IA was suitable for treatment with the device. The investigator successfully placed the device within the IA. In addition, the subject required and received further treatment with another endovascular device(s). The subject is considered enrolled for the purposes of the study and will be followed for the duration of the study.

The available sizes of the Contour implant along with coordinating aneurysm dimensions and definitions are provided in Figure 3.

| REF (Catalog Number) – Diameter | Aneurysm Neck (mm) | Aneurysm Width (mm) |
|------------------------------------|-----------------------|------------------------|
| CNS05 – 5 mm | 2.0 - 3.0 | 2.0 - 3.5 |
| CNS07 – 7 mm | 3.0 - 5.0 | 3.0 - 5.5 |

| Cerus Endovascular | Document Number DNX099-01 | Rev F | Page 33 of 106 |

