10.3 General Principles

The analysis for all primary and secondary study endpoints and baseline, procedural and follow-up characteristics will be performed on an intent-to-treat analysis population which will include all available data for all enrolled subjects. Standard summary statistics will be calculated for all study variables.

The primary safety endpoint will be calculated as the proportion of subjects with death of any nonaccidental cause or any major stroke within the first 30 days after treatment or major stroke or death due to neurological case from day 31 to 6 months after treatment.

The primary performance endpoint will be calculated as the proportion of subjects with complete occlusion demonstrated with a Grade 1 on the Raymond Roy Scale at 6 months.

For AE reporting, both subject counts and event counts will be presented in tabular summaries of results.

A summary of subjects with protocol deviations will be reported but those subjects will be included in all analyses although endpoints may be summarized without the subjects (per-protocol analysis group) to provide additional information but not for the primary analysis.

For continuous variables, statistics will include means, standard deviations, medians and ranges. Categorical variables will be summarized in frequency distributions. Missing data will not be imputed. The number of data values available for each analysis will be reported so that the impact of missing data can be seen.

Statistical analyses will be conducted in SAS version 9.4 or above (SAS Institute, Cary, N.C.).

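### The plan's available-case rule drops deaths and the SAP's own study failures from the primary occlusion rate, and the analysis set behind that rate is contradictory

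*SAP*

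**What the plan says.** **The endpoint.** SAP 7 defines the primary performance endpoint as the "proportion of subjects with complete occlusion demonstrated with a Grade 1 on the Raymond Roy Scale at 6 months", as read by the core laboratory. It names no denominator.

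**Missing grades.** SAP 6 bases all primary and secondary analyses on an "intent-to-treat analysis population which will include all available data for all enrolled subjects", and adds "Missing data will not be imputed". Protocol 10.3 has the same rule and continues: "The number of data values available for each analysis will be reported so that the impact of missing data can be seen". Protocol 10.7 aims for 30 patients with evaluable 6-month data.

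**The analysis set.**
- Protocol 10.2 and SAP 5: "The ITT population includes all patients". Under Protocol 7.5 and the SAP synopsis, enrolment happens at consent.
- Protocol 7.5 uses "The patient is considered enrolled and included in the primary analysis group in the study" for subjects in whom the device was successfully placed. Failed attempts are enrolled but outside that group.
- The SAP synopsis says a patient is "considered a study subject in the reporting analysis group only when the patient is fully qualified" and at least one Contour has been placed in the body.

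**Deaths and study failures.** SAP 5 keeps in the per-protocol set subjects who "die prior to their 6-month clinic visit, or are study failure (withdrawal from study to obtain alternate treatment"). No sentence says how such a subject enters the occlusion rate.

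**The concern.** Withdrawal for alternate treatment is informative about how the device performed. Under the available-case rule, a subject whom the SAP labels a failure disappears from the performance rate instead of counting against it. A subject who dies before the angiogram disappears in the same way. Neither is replaced (Protocol 11.3).

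The second problem is independent of the first. Even with complete grading rules, an analyst has to choose between a denominator of consented subjects, of successful placements, and of subjects with a device placed in the body. The last could include a failed attempt.

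At stake is the main performance figure in the CE Mark submission. The protocol has no hypothesis test and leaves the assessment to clinical judgement, so the point estimate carries the performance message and should be fixed in advance.

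**Working it through.** **Inputs from the plan.** At most 35 subjects are enrolled to obtain 30 with follow-up data (synopses), which leaves room for 35 − 30 = 5, or 5/35 = 14.3%. The plan states no occlusion rate, attrition rate, alpha or power, so there is no calculated figure to reproduce. Every success and loss count below is an assumption.

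**Direction.** Let x be the number of Grade 1 subjects, g the number graded, and m the implanted subjects lost to death or alternate treatment before the angiogram. The available-case rate is x/g. With the m subjects scored as non-success it is x/(g + m). For x > 0 and m > 0 the first is always larger. This compares two scoring rules; it does not measure bias against the unknown true occlusion status.

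**Size with 20 Grade 1 among 30 graded (Clopper-Pearson 95% intervals).**

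| m | Rate | 95% CI |
|---|---|---|
| 0 | 20/30 = 66.7% | 47.2 to 82.7 |
| 1 | 20/31 = 64.5% | 45.4 to 80.8 |
| 2 | 20/32 = 62.5% | 43.7 to 78.9 |
| 3 | 20/33 = 60.6% | 42.1 to 77.1 |

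The interval at m = 0 is 82.7 − 47.2 = 35.5 points wide; the shift at m = 3 is 66.7 − 60.6 = 6.1 points.

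**Range over other assumed rates, m = 3.**
- 15/30 = 50.0% becomes 15/33 = 45.5%, a drop of 4.5 points.
- 25/30 = 83.3% becomes 25/33 = 75.8%, a drop of 7.6 points (from unrounded values).

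**If such subjects used up the whole allowance of five, all implanted.**
- 15/30 = 50.0% becomes 15/35 = 42.9%, a drop of 7.1 points.
- 24/30 = 80.0% becomes 24/35 = 68.6%, a drop of 11.4 points.

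**One assumed data set, several rates.** Suppose 35 are enrolled and 33 successfully implanted. Of the 33, 30 are graded (20 Grade 1), two die or withdraw for alternate treatment, and one angiogram is missing for another reason.
- Available cases: 20/30 = 66.7%.
- Deaths and study failures as non-success: 20/(30 + 2) = 20/32 = 62.5%.
- All successful placements, every missing grade as non-success: 20/33 = 60.6%.
- All enrolled, every subject without a Grade 1 as non-success: 20/35 = 57.1% (39.4 to 73.7).

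The gap between 30 and 33 comes from the missing-grade rule, and the gap between 33 and 35 from the contradictory analysis set.

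**The case against.** **The plan does choose, for missing grades.** A reader might infer that the SAP is evenly split between available-case and non-success scoring, because SAP 5 uses the term study failure. The documents do not support that. The phrase only defines who belongs to the per-protocol set and scores nothing, and SAP 8 says the per-protocol summary is not for the primary analysis. Available data, no imputation and an evaluable target of 30 all lean clearly to available cases. This stands: the first problem is the consequence of the rule that the plan leans to, and the lack of a single definition comes mainly from the analysis-set conflict.

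**Other rates can be rebuilt.** The available n, retreatment, failed attempts, discontinuation and subject listings are all to be reported. This also stands, so nothing is hidden. But disclosure does not settle which rate is the headline.

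**The scenario is narrow.** The enrolment scenarios mention alternative treatment only after failed placement, and Protocol 7.5 already puts those subjects outside the primary analysis group. An implanted subject who is retreated but stays and is imaged still has a grade. The loss arises only where no 6-month core-laboratory reading exists. SAP 5 provides for such withdrawals, but the plan does not say how many to expect.

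**Scoring every missing angiogram as failure would penalise the device for unrelated missed scans.** This is a fair objection, and it is why that rule belongs in a sensitivity analysis.

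**The protocol synopsis appears to place some failed attempts inside the primary analysis group.** The text there is garbled, possibly by the conversion from PDF, so no weight is put on it.

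**Conclusion.** The point holds in two parts. First, the available-case rule removes deaths and withdrawals for alternate treatment before the angiogram from the primary occlusion rate, which favours the device compared with scoring them as non-success. Second, the plan's statements of the analysis set cannot all be true of one rate.

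On the assumed 20/30, one to three such subjects move the rate by 2.2 to 6.1 points; with none it is unchanged. These sizes rest on assumed counts and are small beside the sampling uncertainty.

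A reader might go further and infer that the reported rate will overstate true occlusion, or that the study's conclusion is unsafe. Neither follows. The lost subjects' true status is unknown, their number is not predicted, and Protocol 10 and 10.7 set no test, threshold or power. The change should be made because it is cheap and fixes the definition of the main performance figure; it does not decide whether the study succeeds.

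**What to change.** 1. Reconcile SAP 5 and 6 (and Protocol 10.2 and 10.3) with Protocol 7.5, and name one denominator for the primary occlusion rate: subjects in whom a Contour was successfully placed.
2. In the primary analysis, score death before the 6-month angiogram and withdrawal for alternate treatment as non-success. State that this is part of the endpoint definition, so that it does not clash with the no-imputation rule for other missing angiograms.
3. Report three sensitivity rates: observed cases only; every missing angiogram as non-success; and all subjects with an implant attempt, with failed placements as non-success. The last restores the subjects whom the chosen denominator leaves out.
4. Record the reason for each missing 6-month angiogram. Protocol 7.10 does not list alternate treatment among the withdrawal reasons, and the discontinuation form in Protocol 7.12 does not cover a subject who stays in the study but misses the scan.

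**Cost:** SAP wording with matching protocol text, a few output lines and one reason field. The headline rate may be slightly lower.
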